7.6 Health-Related Quality of Life (HRQoL)

Patients will be asked to complete the NCCN/FACT Symptom Index for Kidney Cancer (FKSI-19), 3-level version of the EuroQol Group's EQ-5D (EQ-5D-3L), and selected items from the Patient-Reported Outcomes version of the Common Term Criteria for Adverse Events (PRO-CTCAE).

Patients will complete the patient-reported outcome measures prior to any assessments at each clinic visit before randomization, prior to the first dose on Day 1 and 22 of every cycle through Cycle 4, and then on Day 1 of all subsequent cycles. In addition, the patient-reported outcome measures will be completed at designated time points during the follow-up period. The primary time points of interest will be Week 12, Week 24, and Week 48.

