EQ-5D-3L	X		X	X	X	Patients should complete the assessment at the start of the clinic visit, prior to dosing and scheduled activities.
FKSI-19	X		X	X	X	
PRO-CTCAE	X		X	X	X	Completed on Days 1 and 22 of every cycle through Cycle 4, and then on Day 1 of the following cycles. See Section 7.6 for further details.

Abbreviations used in this table appear on the final page of [Table 4](#).

Table 3: On-Treatment Schedule of Events for Arm B (Contd)

Procedure ^a	Arm B Cabozantinib 60 mg PO once daily (continuously) OR Sunitinib 50 mg PO once daily (4 weeks on treatment, followed by 2 weeks off treatment) Cycle = 6 Weeks					Notes
	Cycle 1			Cycle 2 and subsequent on-treatment visits		
	Day 1	Day 8 (-1 day)	Day 22 (± 3 days)	Day 1 (± 3 days)	Day 22 (± 3 days)	
Health Care Resource Utilization	X		X	X	X	Site staff will collect the health care resource utilization data at each visit using the CRF.

a. Assessments and visits that occur outside of protocol-specified windows (e.g., for holidays, travel issues, insurance issues) may be acceptable on a case-by-case basis after review by the Medical Monitor.

Abbreviations used in this table appear on the final page of [Table 4](#).

Table 4: Long-Term Follow-Up Schedule of Events

Procedure ^a	Safety Follow-Up Visit 1 ^b	Safety Follow-Up Visit 2 ^b	Survival Follow-Up ^c Every 12 Weeks (± 14 days)	Notes ^d
Safety Assessments				
Vital Signs	X	X		Blood pressure, heart rate, temperature Weight
AE and SAE Assessments	X	X	X	All AEs will be documented until 100 days after the last dose of all study drug(s). SAEs to be collected after the 100-day safety visit if the SAE is deemed to be related or residual toxicities are persisting. Patients will be followed for drug-related toxicities until these toxicities resolve, return to baseline, or are deemed irreversible.
Karnofsky Performance Status	X	X		See Appendix 2 .
Review of Subsequent Medications and Anticancer Therapy	X	X	X	In Survival Follow-up, subsequent anticancer treatment only. Additional subsequent anticancer therapy details such as regimen, setting of the regimen, line of therapy, start date and end date of each regimen, best response to the regimen, and date of progression to subsequent anticancer therapies will be collected.
Laboratory Tests				
Pregnancy Test (WOCBP only)	X	X		Patients (WOCBP) will continue to follow instructions for methods of contraception through 5 months post treatment completion.

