5.4.1.3 Sunitinib and Cabozantinib Dosing

Sunitinib will be administered on a 6-week cycle, starting at a dose of 50 mg once daily for 4 weeks, followed by 2 weeks of no treatment. Cabozantinib will be administered at a starting dose of 60 mg once daily; for patients with moderate hepatic impairment (Child Pugh Class B) the starting dose of cabozantinib will be 40 mg once daily. Food fasting is recommended for 2 hours before and 1 hour after cabozantinib administration. [Table 7](#) provides the permitted doses for sunitinib and cabozantinib. Refer to the sunitinib ([Sutent[®]](#)) and cabozantinib ([Cabometyx[®]](#)) US Prescribing Information and/or the corresponding SmPC for updated dosing guidance or further information.

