5.13 Dosage Modification

Every effort should be made to follow planned dosing schedules for all study drugs in both treatment arms. Study drug administration may be delayed or modified for toxicity as described below and must be discontinued as required by criteria described in Section 5.14.

Dose modification for NKTR-214 and nivolumab in Arm A may be considered independently based on Investigator assessment of relationship of a toxicity to each of the study drugs. If only one of the study drugs meets the criteria for dose delay, then administration of the other study drug may be continued or delayed at the discretion of the Investigator. Likewise, in the event that one of the study drugs in Arm A is permanently discontinued due to toxicities, the other can continue to be administered.

Patients who require delay of nivolumab or NKTR-214 should be re-evaluated weekly or more frequently if clinically indicated and should resume treatment with combination of NKTR-214 and nivolumab when retreatment criteria are met (Section 5.13.7). Immuno-oncology agents are associated with AEs that can differ in severity and duration from AEs caused by other therapeutic classes. NKTR-214 and nivolumab are considered an immuno-oncology agent in this protocol. Early recognition and management of AEs associated with immuno-oncology agents may mitigate severe toxicity.

For patients randomized to Arm A: NKTR-214 or nivolumab administration defines a scheduled nominal dosing visit (i.e., Cycle X Day 1, Cycle X Day 22). If a patient is assessed for an intended nominal dosing visit but study drug is not administered (e.g., due to an AE requiring dose delay, drug unavailable), any assessments performed during that visit should be recorded as “unscheduled.” When study drug administration resumes, all assessments should be performed as scheduled for the next nominal dosing visit (i.e., Cycle X Day 1 or Cycle X Day 22 Visit).

For patients randomized to Arm B: Cycle 1 Day 1 is defined by the date that the first dose of sunitinib or cabozantinib is administered. Within a cycle, missed doses of sunitinib should be skipped and not replaced. Scheduled Cycle X Day 1 and Cycle X Day 22 visits are fixed relative to Cycle 1 Day 1, regardless of dose delays. If drug dosing is delayed at the time of these scheduled visits (e.g., due to an AE requiring dose delay, drug unavailable), the cycle visit is not shifted and all assessments should be performed as scheduled.

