5.0 OVERALL STUDY DESIGN AND PLAN

5.1 Study Design

This is a multicenter, randomized, open label, Phase 3 study that will evaluate the efficacy and safety of NKTR-214 combined with nivolumab compared with the Investigator's choice of a TKI, either sunitinib or cabozantinib, in patients with previously untreated advanced RCC.

The treatment period of the study is divided into multiple treatment cycles with associated evaluations and procedures. One cycle of treatment is defined as 6 weeks. Results of the assessments must be reviewed and documented before administering the scheduled dose of study drugs. In certain circumstances, patients with progressive disease (PD) per mRECIST 1.1 but with otherwise stable or improved performance and clinical status may continue to be treated in the event of a perceived benefit per Investigator.

This study is divided into a Screening period, a Treatment period, and a Long-Term Follow-Up period, which will continue until withdrawal of consent, death, lost to follow-up, or study termination by the Sponsor.

Approximately 600 patients (including at least 500 patients with IMDC intermediate- or poor-risk and approximately 100 patients with IMDC favorable risk) with previously untreated advanced RCC will be randomized in a 1:1 ratio to the two treatment arms below:

- Arm A: NKTR-214 0.006 mg/kg IV Q3W combined with nivolumab 360 mg IV Q3W
- Arm B: Investigator's choice of either one of the following treatments
 - Sunitinib 50 mg po once daily for 4 weeks followed by 2 weeks offOR
 - Cabozantinib 60 mg po once daily

Randomization will be stratified by:

- IMDC prognostic score (0 [favorable risk] versus 1-2 [intermediate risk] versus 3-6 [poor risk]); laboratory data used to calculate IMDC score are based on central laboratory results)
- TKI choice (sunitinib versus cabozantinib)

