6.7 Study Drug Exposure

For NKTR-214 and nivolumab in Arm A, the following parameters will be calculated:

- Exposure duration (days) for each drug: Date of last dose – date of first dose (C1D1) + 1

For NKTR-214 in Arm A, the following parameters will be calculated:

- Total number of infusions: Total number of infusions for which the patient received a non-zero dose across all cycles

- Cumulative dose (mg/kg): Total actual dose (mg/kg) the patient received across all cycles, defined as the sum of actual doses (mg/kg) received across all cycles
- Average dose per infusion (mg/kg): Cumulative dose (mg/kg) / Total number of infusions
- Average duration of infusion (min): Total infusion time (min) / Total number of infusions; where total infusion time = summation of (completion time of infusion – start time of infusion) for all infusions of a patient
- Actual dose intensity (mg/kg/week): [Cumulative dose (mg/kg) / (Exposure duration (in days) + 20 days)] × 7
- Expected dose intensity (mg/kg/week) = (0.006 mg/kg) / (3 weeks) = 0.002 mg/kg/week
- Relative dose intensity (%): (Actual dose intensity / Expected dose intensity) × 100

For Nivolumab in Arm A, the following parameters will be calculated:

- Total number of infusions: Total number of infusions for which the patient received a non-zero dose across all cycles
- Cumulative dose (mg): Total actual dose (mg) the patient received across all cycles, defined as the sum of actual doses (mg) received across all cycles
- Average dose per infusion (mg): Cumulative dose (mg) / Total number of infusions
- Average duration of infusion (min): Total infusion time (min) / Total number of infusions; where total infusion time = summation of (completion time of infusion – start time of infusion) for all infusions of a patient
- Actual dose intensity (mg/week): [Cumulative dose (mg) / (Exposure duration (in days) + 20 days)] × 7
- Expected dose intensity (mg/week) = (360 mg) / (3 weeks) = 120 mg/week
- Relative dose intensity (%): (Actual dose intensity / Expected dose intensity) × 100

For Sunitinib in Arm B, the following parameters will be calculated:

- Exposure duration (days): Date of last dose – date of first dose (C1D1) + 1
- Total number of doses: Total number of doses the patient received
- Average daily dose (mg/day): Sum of all sunitinib doses in mg actually received / Exposure of duration (in days)
- Expected daily dose (mg/day): 33.33 mg/day (= 50 mg × 28 days / 42 days)

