(Note that sunitinib treatment consists of 50 mg PO daily dose for 4 weeks followed by 2 weeks of a washout period)
- Relative dose intensity (%): (Average daily dose / Expected daily dose) × 100

For Cabozantinib in Arm B, the following parameters will be calculated:

- Exposure duration (days): Date of last dose – date of first dose (C1D1) + 1
- Total number of doses: Total number of doses the patient received
- Average daily dose (mg/day): Sum of all cabozantinib doses in mg actually received / Exposure of duration (in days)
- Expected daily dose (mg/day): 60 mg/day or 40 mg/day (40 mg for patients with mild to moderate hepatic impairment [Child-Pugh score A or B])
- Relative dose intensity (%): $(\text{Average daily dose} / \text{Expected daily dose}) \times 100$

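### All three named quality-of-life time points follow sunitinib's two-week break, so the FKSI-19 recall period at each contains no on-drug days for those patients

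*SAP*

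**What the plan says.** SAP 7.6 schedules the questionnaires on Days 1 and 22 of Cycles 1 to 4, "and then on Day 1 of all subsequent cycles", and singles out three visits: "The primary time points of interest will be Week 12, Week 24, and Week 48". SAP 5.1 fixes the cycle: "One cycle of treatment is defined as 6 weeks".

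Protocol 5.4.1.3 describes sunitinib as "starting at a dose of 50 mg once daily for 4 weeks, followed by 2 weeks of no treatment". SAP 6.7 calls the same gap a washout: "Note that sunitinib treatment consists of 50 mg PO daily dose for 4 weeks followed by 2 weeks of a washout period". For Arm B, Protocol 5.13 adds "Scheduled Cycle X Day 1 and Cycle X Day 22 visits are fixed relative to Cycle 1 Day 1, regardless of dose delays", and says that sunitinib doses missed within a cycle are skipped, not made up. Cabozantinib is taken daily without a break.

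The schedules of events in Protocol 1.2 put the questionnaires before treatment: "Patients should complete the assessment at the start of the clinic visit, prior to dosing and scheduled activities". FKSI-19 and PRO-CTCAE ask about the past week; EQ-5D-3L asks about the same day (SAP 7.6.1 to 7.6.3). FKSI-19 total and subscale scores are summarised at every assessment and compared between arms with a mixed model for repeated measures that includes a treatment-by-time term (SAP 7.6.1). Neither SAP 7.6 nor Protocol 7.6 mentions the sunitinib off period.

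**The concern.** Naming primary time points tells the reader where the headline FKSI-19 comparison will be read. SAP 7.6.1 says that the arms will be compared by a difference in least-square means but not at which visits, so the three named weeks are the natural choice. If all three sit at the same phase of an on/off schedule, the headline describes that phase only.

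FKSI-19 supports a stated secondary objective and has a treatment side-effects subscale. Protocol 2.4.1 lists fatigue, diarrhea, nausea and mucositis among the common reactions to sunitinib, all of which a patient could report. Any such symptoms limited to the weeks on drug would not appear at the named visits, and nothing in the quality-of-life sections would warn the reader.

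**Working it through.** **Inputs.** Cycle length 42 days (SAP 5.1). Sunitinib on cycle days 1–28 and off on days 29–42 (Protocol 5.4.1.3; SAP 6.7). FKSI-19 recall 7 days (SAP 7.6.1), completed before dosing (Protocol 1.2). Visit window ±3 days (Protocol 1.2). First dose 0 to 5 days after randomization (Protocol 5.4.1).

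**Plan's own figure.** SAP 6.7 gives sunitinib's expected daily dose as 33.33 mg/day. 50 × 28 / 42 = 33.33, so the SAP uses the same 28/42-day pattern.

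**Mapping weeks to cycle days.** Week w falls on dosing day d = 7w + 1. The cycle number is the whole part of (d − 1)/42, plus 1; the cycle day is the remainder plus 1. The recall period is the 7 days before the visit.

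| Week | Dosing day | Visit | Recall (cycle days) | On-drug days |
|---|---|---|---|---|
| 9 | 64 | Cycle 2 Day 22 | 15–21 of Cycle 2 | 7 of 7 |
| 12 | 85 | Cycle 3 Day 1 | 36–42 of Cycle 2 | 0 of 7 |
| 21 | 148 | Cycle 4 Day 22 | 15–21 of Cycle 4 | 7 of 7 |
| 24 | 169 | Cycle 5 Day 1 | 36–42 of Cycle 4 | 0 of 7 |
| 48 | 337 | Cycle 9 Day 1 | 36–42 of Cycle 8 | 0 of 7 |

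**Does the visit window change this?** Each source of slack was varied separately.
- Day 1 visit 3 days early: recall covers days 33–39, 0 of 7.
- Day 1 visit 3 days late: 0 of 7 if dosing restarts at the visit; at most 3 of 7 if it restarted on nominal Day 1.
- Weeks counted from randomization with a 0 to 5 day lag: 0 of 7 in every case.
- Day 22 visit 3 days early or late: recall covers days 12–18 or 18–24, all within days 1–28, so 7 of 7.

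**All visits through Week 48.** Under SAP 7.6 there are 12 post-baseline visits: Day 1 of Cycles 2 to 9 (8 visits, 0 of 7 on drug) and Day 22 of Cycles 1 to 4 (4 visits, 7 of 7). No visit after Week 21 covers an on-drug week.

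**Arm A at the same visits.** Infusions are three weeks apart. Counting the infusion as day 1, the next dosing visit is day 22 and its pre-dose recall covers days 15–21. At the minimum 18-day gap (Protocol 5.4.1.1) it covers days 12–18. Protocol 2.2.4 puts IL-2 mediated events generally 3 to 4 days after dosing. Protocol 5.13.4 puts peak active cytokine at Days 4–8, often with flu-like symptoms, rash or pruritus. Protocol 5.15.3.5 says that the cytokine rise lasts about a week. Arm A's recall misses that window at Day 1 and at Day 22 alike.

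**The case against.** A reader might infer that the named visits bias the comparison toward the control arm, because sunitinib is seen at its best. The documents do not support that. Arm A is also assessed at a quiet point in its dosing interval, so its own acute symptoms are missed too. No section gives the within-cycle timing of sunitinib symptoms, so how quickly they fade off drug would have to come from outside. Symptoms that persist into the break are still reported on Day 1.

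A second tempting reading is that on-drug symptoms are lost from the quality-of-life plan altogether. They are not. Day 22 scores from Cycles 1 to 4 are summarised and plotted, and nothing confines the mixed model to Weeks 12, 24 and 48. SAP 7.6.3 reports PRO-CTCAE as each patient's maximum post-baseline score, which does not depend on the named weeks.

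It is also fair to say that the consequence is limited. FKSI-19 is an other-secondary endpoint with no alpha, outside the testing hierarchy, and no decision turns on these weeks. Day 22 is not neutral either: it sets sunitinib on drug against Arm A before dosing, which could favour Arm A. Averaging a Day 22 with the next Day 1 would weight on-drug time at 1/2, whereas sunitinib is taken on 28/42 = 2/3 of days.

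All of this stands. It rules out a claim of known direction and a switch to Day 22 alone. It does not answer the narrower point that every named time point falls at the same off-drug phase and the SAP does not say so.

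**Conclusion.** The point holds as a minor one about which visits are named. For sunitinib patients on the planned schedule, all three named time points have 0 of 7 on-drug recall days, against 7 of 7 at Day 22 visits that are already collected. EQ-5D-3L asks about the day itself, which at these visits is a pre-dose day after 14 days off, so the same limit applies to it.

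The conclusion assumes that patients follow the 4-weeks-on, 2-weeks-off pattern and that visits stay tied to first dose, as Protocol 5.13 requires. It covers only the sunitinib share of Arm B, which the documents do not give. The effect on scores cannot be derived from the documents, and the sign of any net between-arm bias is undetermined.

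**What to change.** In SAP 7.6, add Weeks 9 and 21 (Day 22 of Cycles 2 and 4) to the named time points. Report the treatment difference from the existing FKSI-19 mixed model at Weeks 9 and 21 beside Weeks 12 and 24. Keep Week 48, which has no on-drug counterpart under the SAP's collection schedule. Do not define a pair average.

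Add a short statement that Day 1 recall excludes sunitinib's on-drug weeks and that neither visit type covers Arm A's acute post-infusion window. Make the change before database lock, so that the choice of visits is not made after seeing results.

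The cost is SAP wording and a few output rows, with no new questionnaires, visits or protocol change. The drawback is that the Day 22 contrast compares sunitinib on drug with Arm A before dosing, so the two visit types must be read together and neither taken alone.

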7.6.1 FKSI-19

The National Comprehensive Cancer Network/Functional Assessment of Cancer Therapy–Kidney Symptom Index-19 (FKSI-19) is a 19-item self-reported questionnaire with a total score and four subscales that assess disease-related symptoms (DRS), treatment side effects (TSE), and function/well-being associated with advanced kidney cancer. It captures symptom severity and interference in activity and general health perceptions. The FKSI-19 comprises four subscales (DRS-Physical, DRS-Emotional, TSE, and Function/Well-Being). Each of the items is scored on a five-point scale from zero (not at all) to four (very much). The FKSI-19 uses a recall period of “the past 7 days”, and higher FKSI-19 scores indicate improvement ([Rothrock, 2013](#)).

If there are missing items, subscale scores can be prorated. This can be done using the following formula:

$$\text{Prorated subscale score} = [\text{Sum of item scores}] \times [\text{N of items in subscale}] / [\text{N of items answered}]$$

When there are missing data, prorating by subscale in this way is acceptable as long as more than 50% of the items were answered in that subscale; otherwise the subscale is considered as not

having a valid score. The total score is then calculated as the sum of the prorated subscale scores. The total score should only be calculated if ALL of the component subscales have valid scores.

The following descriptive analyses will be conducted by treatment group in the ITT I/P-risk population and the ITT all-risk population:

- FKSI-19 questionnaire completion rate, defined as the proportion of questionnaires actually received out of the expected number (ie, number of patients on treatment or in follow up), will be calculated and summarized for each assessment time point.
- For the total score and subscales, separately:
 - Mean score and mean change from baseline at each assessment time point will be summarized using descriptive statistics (N, mean, SD, median, 25th and 75th percentiles, minimum, maximum).
 - A plot summarizing the mean change from baseline will be presented.
 - Changes from baseline will be compared between treatment groups using a linear mixed model with repeated measures (MMRM) with treatment, time, treatment and time interaction, baseline score, and stratification variables as covariates. An unstructured covariance matrix will be used unless the model fails to converge. Treatment effect on the change from baseline will be compared by the difference in the least-square means and corresponding 95% CI. The MMRM assumes that the missing data mechanism is ignorable (i.e., missing at random).

7.6.2 EQ5D3L

The EQ-5D-3L is a standardized instrument used to measure self-reports of health status and functioning. The instrument's descriptive system consists of 5 dimensions: mobility, self-care, usual activities, pain/discomfort, and anxiety/depression. Each dimension has 3 levels, reflecting "no health problems," "moderate health problems," and "extreme health problems." A dimension for which there are no problems is said to be at level 1, while a dimension for which there are extreme problems is said to be at level 3. Thus, the vectors 11111 and 33333 represent the best health state and the worst health state, respectively, as described by the EQ-5D-3L. Altogether, the instrument describes $3^5 = 243$ health states (EuroQol, 1990).

Empirically-derived weights can be applied to an individual's responses to the EQ-5D-3L descriptive system to generate an index measuring the value to society of his or her current health. Such preference-weighting systems have been developed for the UK, US, Spain, Germany, and numerous other populations. Utility index values range from a 1 (full health) to 0 (dead) with negative values indicating a state considered worse than being dead. In addition, the EQ-5D-3L includes a visual analog scale (VAS) that allows respondents to rate their own current health on a 101-point scale ranging from "best imaginable" to "worst imaginable" health. The EQ-5D-3L uses a recall period of "today."

EQ-5D Index values will be computed using a scoring algorithm based on the US TTO (Time Trade-off) value set. The following descriptive analyses will be conducted:

- EQ-5D questionnaire completion rate, defined as the proportion of questionnaires actually received out of the expected number (ie, number of patients on treatment or in follow up), will be calculated and summarized for each assessment time point.
- A by-patient listing of EQ-5D with the problem level for each of the 5 dimensions (mobility, selfcare, usual activities, pain/discomfort and anxiety/depression), health state (5 dimensions digits combined in a 5-digit number), EQ-5D Index, and EQ-VAS will be provided.
- Proportion of patients for each level of problem for the 5 EQ-5D dimensions will be summarized at each assessment timepoint. Percentages will be based on number patients assessed at assessment time point.
- For the EQ-5D Index and visual analog scale (VAS), separately:
 - Mean score and mean change from baseline at each assessment time point will be summarized using descriptive statistics (N, mean, SD, median, 25th and 75th percentiles, minimum, maximum).
 - A plot summarizing the mean change from baseline will be presented.

